Appendix 13.4 One of the following blood count abnormalities

The search will use laboratory blood sample values along with their corresponding reference ranges

- Lymphocytes above or below lab limits
- Eosinophils above the lab limits
- Platelets below lab limits

Appendix 13.5 Fever above 38 degrees Celsius

The following selection will be performed based on AE

- Hyperthermia
- Hyperpyrexia
- Pyrexia
- Febrile bone marrow aplasia (and all PTs that include the word “febrile”)
- Body temperature increased
- Body temperature abnormal

Appendix 14 Overview of primary, secondary and exploratory efficacy objectives

Objective Clinical Category	Statistical Category	Estimand/Variable
Primary Objective: To evaluate the effect of multiple doses of nabiximols as adjunctive therapy compared with placebo on a clinical measure of velocity-dependent muscle tone in the lower limbs (Lower Limb Muscle Tone-6; LLMT-6) in patients with multiple sclerosis (MS) who have not achieved adequate relief from spasticity with other antispasticity medications.		
LLMT-6	P1, Primary	Variable: Change from period baseline in LLMT-6 at D21 Population: FAS Regardless permanent treatment discontinuation Regardless premature study discontinuation Regardless major IPD Accounting for COVID-19 impact PLS: Mean difference between nabiximols and placebo Analysis: LSMD from CFB linear mixed-effect model for crossover data adjusted on period baseline LLMT-6 with placebo-based MI under MNAR assumption.
	P1, SA1 (Sensitivity)	Variable: Change from period baseline in LLMT-6 at D21 Population: FAS Regardless permanent treatment discontinuation Regardless premature study discontinuation Regardless major IPD Accounting for COVID-19 impact PLS: Mean difference between nabiximols and placebo Analysis: LSMD from CFB linear mixed-effect model for crossover data adjusted on period baseline LLMT-6 with MI under MNAR assumption. Tipping point analysis
	P1, SUP1 (Supplementary, Subgroup)	Subgroup analyses based on same estimand as primary endpoint
	P1, SUP2 (response analyses)	Variable: proportion of patients with LLMT-6 score reduction criterion cut-offs defined by different percentages of $\geq 20\%$, $\geq 30\%$, $\geq 40\%$, $\geq 50\%$ from period baseline in LLMT-6 at D21 Population: FAS IES: Regardless permanent treatment discontinuation Regardless premature study discontinuation Regardless major IPD Regardless COVID-19 impact PLS: Odd ratio in nabiximols versus placebo Analysis: OR from logistic regression model for crossover data adjusted on period baseline LLMT-6. Single imputation: Missing D21 values are imputed a failure.

	P1, SUP 3 (Repeated measure analysis)	Variable: Change from period baseline in LLMT-6 at D21 Population: FAS IES: Regardless permanent treatment discontinuation Regardless premature study discontinuation Regardless major IPD Regardless deviation from time window at D1H3 Accounting for COVID-19 impact PLS: Mean difference between nabiximols and placebo Analysis: LSMD from CFB linear mixed-effect model with repeated measure for crossover data adjusted on period baseline LLMT-6 with placebo-based MI under MNAR assumption.
	P1, SUP4 (Supplementary without missing individual muscle group MAS score)	Variable: Change from period baseline in LLMT-6 at D21 Population: Study completer analysis set IES: Regardless permanent treatment discontinuation Without premature study discontinuation Regardless major IPD Accounting for COVID-19 impact Excluding LLMT-6 score derived with missing individual muscle group MAS score PLS: Mean difference between nabiximols and placebo Analysis: LSMD from CFB linear mixed-effect model for crossover data adjusted on period baseline LLMT-6 with placebo-based MI under MNAR assumption.
	P1, SUP5 (Supplementary without premature study discontinuation)	Variable: Change from period baseline in LLMT-6 at D21 Population: Study completer analysis set IES: Regardless permanent treatment discontinuation Without premature study discontinuation Regardless major IPD Accounting for COVID-19 impact PLS: Mean difference between nabiximols and placebo Analysis: LSMD from CFB linear mixed-effect model for crossover data adjusted on period baseline LLMT-6 with placebo-based MI under MNAR assumption.
	P1, SUP6 (Supplementary on-treatment assessment)	Variable: Change from period baseline in LLMT-6 at D21 Population: FAS IES: Prior permanent treatment discontinuation Regardless premature study discontinuation Without major IPD Accounting for COVID-19 impact PLS: Mean difference between nabiximols and placebo Analysis: LSMD from CFB linear mixed-effect model for crossover data adjusted on period baseline LLMT-6 with placebo-based MI under MNAR assumption.

	P1, SUP7 (Supplementary without major IPD impact)	Variable: Change from period baseline in LLMT-6 at D21 Population: PP analysis set IES: Regardless permanent treatment discontinuation Prior to major IPD Accounting for COVID-19 impact PLS: Mean difference between nabiximols and placebo Analysis: LSMD from CFB linear mixed-effect model for crossover data adjusted on period baseline LLMT-6 with placebo-based MI under MNAR assumption.
	P1, SUP8 (Supplementary without major IPD impact and without deviation from time window)	Variable: Change from period baseline in LLMT-6 at D21 Population: PP analysis set IES: Prior permanent treatment discontinuation Regardless premature study discontinuation Without major IPD Without deviation from time window at D1H3 Accounting for COVID-19 impact PLS: Mean difference between nabiximols and placebo Analysis: LSMD from CFB linear mixed-effect model with repeated measure for crossover data adjusted on period baseline LLMT-6 with placebo-based MI under MNAR assumption.
	P1, SUP9 (Supplementary without COVID-19 impact)	Variable: Change from period baseline in LLMT-6 at D21 Population: FAS IES: Regardless permanent treatment discontinuation Regardless premature study discontinuation Regardless major IPD Without COVID-19 impact PLS: Mean difference between nabiximols and placebo Analysis: LSMD from CFB linear mixed-effect model for crossover data adjusted on period baseline LLMT-6 with placebo-based MI under MNAR assumption.
LLMT-4	S1, Primary	Variable: Change from period baseline in LLMT-4 at D21 Population: FAS IES: Regardless permanent treatment discontinuation Regardless premature study discontinuation Regardless major IPD Accounting for COVID-19 impact PLS: Mean difference between nabiximols and placebo Analysis: LSMD from CFB linear mixed-effect model for crossover data adjusted on period baseline LLMT-4 with placebo-based MI under MNAR assumption.

Secondary objective (efficacy): To evaluate the effect of multiple doses of nabiximols as adjunctive therapy compared with placebo on a clinical measure of velocity-dependent muscle tone in the lower limbs (Lower Limb Muscle Tone 4; LLMT-4) in patients with multiple sclerosis who have not achieved adequate relief from spasticity with other antispasticity medications.

	S1, SA1 (Sensitivity)	Variable: Change from period baseline in LLMT-4 at D21 Population: FAS Regardless permanent treatment discontinuation Regardless premature study discontinuation Regardless major IPD Accounting for COVID-19 impact PLS: Mean difference between nabiximols and placebo Analysis: LSMD from CFB linear mixed-effect model for crossover data adjusted on period baseline LLMT-4 with MI under MNAR assumption. Tipping point analysis
	S1, SUP1 (Repeated measure analysis)	Variable: Change from period baseline in LLMT-4 at D21 Population: FAS IES: Regardless permanent treatment discontinuation Regardless premature study discontinuation Regardless major IPD Regardless deviation from time window at D1H3 Accounting for COVID-19 impact PLS: Mean difference between nabiximols and placebo Analysis: LSMD from CFB linear mixed-effect model with repeated measure for crossover data adjusted on period baseline LLMT-4 with placebo-based MI under MNAR assumption.
	S1, SUP2 (Supplementary without missing individual muscle group MAS score)	Variable: Change from period baseline in LLMT-4 at D21 Population: Study completer analysis set IES: Regardless permanent treatment discontinuation Without premature study discontinuation Regardless major IPD Accounting for COVID-19 impact Excluding LLMT-4 score derived with missing individual muscle group MAS score PLS: Mean difference between nabiximols and placebo Analysis: LSMD from CFB linear mixed-effect model for crossover data adjusted on period baseline LLMT-4 with placebo-based MI under MNAR assumption.
	S1, SUP3 (Supplementary without premature study discontinuation)	Variable: Change from period baseline in LLMT-4 at D21 Population: Study completer analysis set IES: Regardless permanent treatment discontinuation Without premature study discontinuation Regardless major IPD Accounting for COVID-19 impact PLS: Mean difference between nabiximols and placebo Analysis: LSMD from CFB linear mixed-effect model for crossover data adjusted on period baseline LLMT-4 with placebo-based MI under MNAR assumption.

	S1, SUP4 (Supplementary on-treatment assessment)	Variable: Change from period baseline in LLMT-4 at D21 Population: FAS IES: Prior permanent treatment discontinuation Regardless premature study discontinuation Without major IPD Accounting for COVID-19 impact PLS: Mean difference between nabiximols and placebo Analysis: LSMD from CFB linear mixed-effect model for crossover data adjusted on period baseline LLMT-4 with placebo-based MI under MNAR assumption.
	S1, SUP5 (Supplementary without major IPD impact)	Variable: Change from period baseline in LLMT-4 at D21 Population: PP analysis set IES: Regardless permanent treatment discontinuation Regardless premature study discontinuation Without major IPD Accounting for COVID-19 impact PLS: Mean difference between nabiximols and placebo Analysis: LSMD from CFB linear mixed-effect model for crossover data adjusted on period baseline LLMT-4 with placebo-based MI under MNAR assumption.
	S1, SUP6 (Supplementary without COVID-19 impact)	Variable: Change from period baseline in LLMT-4 at D21 Population: FAS IES: Regardless permanent treatment discontinuation Regardless premature study discontinuation Regardless major IPD Without COVID-19 impact PLS: Mean difference between nabiximols and placebo Analysis: LSMD from CFB linear mixed-effect model for crossover data adjusted on period baseline LLMT-4 with placebo-based MI under MNAR assumption.
Exploratory objective: To evaluate the effect of multiple doses of nabiximols as adjunctive therapy compared with placebo on a clinical measure of velocity-dependent muscle tone in the lower limbs (Lower Limb Muscle Tone-10; LLMT-10) in patients with multiple sclerosis who have not achieved adequate relief from spasticity with other antispasticity medications		
LLMT-10	E1, Primary	Variable: Change from period baseline in LLMT-10 at D21 Population: FAS IES: Regardless permanent treatment discontinuation Regardless premature study discontinuation Regardless major IPD Accounting for COVID-19 impact PLS: Mean difference between nabiximols and placebo Analysis: LSMD from CFB linear mixed-effect model for crossover data adjusted on period baseline LLMT-10 with placebo-based MI under MNAR assumption.

	E1, SUP1 (Repeated measure analysis)	Variable: Change from period baseline in LLMT-10 at D21 Population: FAS IES: Regardless permanent treatment discontinuation Regardless premature study discontinuation Regardless major IPD Regardless deviation from time window at D1H3 Accounting for COVID-19 impact PLS: Mean difference between nabiximols and placebo Analysis: LSMD from CFB linear mixed-effect model with repeated measure for crossover data adjusted on period baseline LLMT-10 with placebo-based MI under MNAR assumption
	E1, SUP2 (Supplementary without missing individual muscle group MAS score)	Variable: Change from period baseline in LLMT-10 at D21 Population: Study completer analysis set IES: Regardless permanent treatment discontinuation Without premature study discontinuation Regardless major IPD Accounting for COVID-19 impact Excluding LLMT-10 score derived with missing individual muscle group MAS score PLS: Mean difference between nabiximols and placebo Analysis: LSMD from CFB linear mixed-effect model for crossover data adjusted on period baseline LLMT-10 with placebo-based MI under MNAR assumption.
	E1, SUP3 (Supplementary without premature study discontinuation)	Variable: Change from period baseline in LLMT-10 at D21 Population: Study completer analysis set IES: Regardless permanent treatment discontinuation Without premature study discontinuation Regardless major IPD Accounting for COVID-19 impact PLS: Mean difference between nabiximols and placebo Analysis: LSMD from CFB linear mixed-effect model for crossover data adjusted on period baseline LLMT-10 with placebo-based MI under MNAR assumption.
	E1, SUP4 (Supplementary on-treatment assessment)	Variable: Change from period baseline in LLMT-10 at D21 Population: FAS IES: Prior permanent treatment discontinuation Regardless premature study discontinuation Without major IPD Accounting for COVID-19 impact PLS: Mean difference between nabiximols and placebo Analysis: LSMD from CFB linear mixed-effect model for crossover data adjusted on period baseline LLMT-10 with placebo-based MI under MNAR assumption.

	E1, SUP5 (Supplementary without major IPD impact)	Variable: Change from period baseline in LLMT-10 at D21 Population: PP analysis set IES: Regardless permanent treatment discontinuation Regardless premature study discontinuation Without major IPD Accounting for COVID-19 impact PLS: Mean difference between nabiximols and placebo Analysis: LSMD from CFB linear mixed-effect model for crossover data adjusted on period baseline LLMT-10 with placebo-based MI under MNAR assumption.
	E1, SUP6 (Supplementary without COVID-19 impact)	Variable: Change from period baseline in LLMT-10 at D21 Population: FAS IES: Regardless permanent treatment discontinuation Regardless premature study discontinuation Regardless major IPD Without COVID-19 impact PLS: Mean difference between nabiximols and placebo Analysis: LSMD from CFB linear mixed-effect model for crossover data adjusted on period baseline LLMT-10 with placebo-based MI under MNAR assumption.

Exploratory Objective: To evaluate the effect of nabiximols after administration of multiple doses on walking using the Timed 25-Foot Walk (T25FW) test.

T25FW	E2, Primary	Variable: Change from period baseline in average 25-foot walk time at D21 Population: FAS IES: Regardless permanent treatment discontinuation Regardless premature study discontinuation Regardless major IPD Regardless COVID-19 impact PLS: Mean difference between nabiximols and placebo Analysis: LSMD from CFB linear mixed-effect model for crossover data adjusted on period baseline average T25FW. Single imputation at trial level: missing trial time are imputed to 180 seconds under MAR assumption
-------	--------------------	---

	E2, S1 (without missing trial time imputation)	
Variable: Change from period baseline in average 25-foot walk time at D21
 
Population: FAS
 
IES:
 
 Regardless permanent treatment discontinuation Regardless premature study discontinuation Regardless major IPD Regardless COVID-19 impact 
PLS: Mean difference between nabiximols and placebo
 
Analysis: LSMD from CFB linear mixed-effect model for crossover data adjusted on period baseline average T25FW. No imputation under MAR assumption

	E2, SUP1 (response analysis)	
Variable: proportion of patients with a 20% decrease from period baseline in average T25FW at D21
 
Population: FAS
 
IES:
 
 Regardless permanent treatment discontinuation Regardless premature study discontinuation Regardless major IPD Regardless COVID-19 impact 
PLS: Odd ratio in nabiximols versus placebo
 
Analysis: OR from logistic regression model for crossover data adjusted on period baseline average T25FW. Single imputation: Missing D21 values are imputed a failure.

	E2, SUP2 (Supplementary without major IPD impact)	
Variable: Change from period baseline in average 25-foot walk time at D21
 
Population: PP analysis set
 
IES:
 
 Regardless permanent treatment discontinuation Regardless premature study discontinuation Without major IPD Regardless COVID-19 impact 
PLS: Mean difference between nabiximols and placebo
 
Analysis: LSMD from CFB linear mixed-effect model for crossover data adjusted on period baseline average T25FW. No imputation under MAR assumption

	E2, SUP3 (Supplementary without COVID-19 impact)	
Variable: Change from period baseline in average 25-foot walk time at D21
 
Population: FAS
 
IES:
 
 Regardless permanent treatment discontinuation Regardless premature study discontinuation Regardless major IPD Without COVID-19 impact. 
PLS: Mean difference between nabiximols and placebo
 
Analysis: LSMD from CFB linear mixed-effect model for crossover data adjusted on period baseline average T25FW. No imputation under MAR assumption

Exploratory Objectives: To evaluate the effect of nabiximols after administration of multiple doses on the following patient-reported outcomes: the 11-point Numerical Rating Scale (NRS) spasticity score, Daily spasm count as well as the MS Spasticity Scale (MSSS-88) total and subdomain scores.

11-point NRS-spasticity score	E3, Primary	Variable: 7-day average NSR spasticity score at D21 Population: FAS IES: Regardless permanent treatment discontinuation Regardless premature study discontinuation Regardless major IPD Regardless COVID-19 impact PLS: Mean difference between nabiximols and placebo Analysis: LSMD from observed value linear mixed-effect model for crossover data. No imputation under MAR assumption
	E3, SUP1 (Supplementary without major IPD impact)	Variable: 7-day average NSR spasticity score at D21 Population: PP analysis set IES: Regardless permanent treatment discontinuation Regardless premature study discontinuation Without major IPD Regardless COVID-19 impact PLS: Mean difference between nabiximols and placebo Analysis: LSMD from observed value linear mixed-effect model for cross over data. No imputation under MAR assumption
	E3, SUP2 (Supplementary without COVID-19 impact)	Variable: 7-day average NSR spasticity score at D21 Population: FAS IES: Regardless permanent treatment discontinuation Regardless premature study discontinuation Regardless major IPD Without COVID-19 impact. PLS: Mean difference between nabiximols and placebo Analysis: LSMD from observed value linear mixed-effect model for crossover data. No imputation under MAR assumption
7-days average daily spasm count	E4, Primary	Variable: 7-days average daily spasm count at D21 Population: FAS IES: Regardless permanent treatment discontinuation Regardless premature study discontinuation Regardless major IPD Regardless COVID-19 impact PLS: Mean difference between nabiximols and placebo Analysis: LSMD from observed value linear mixed-effect model for crossover data. No imputation under MAR assumption

	E4, SUP1 (Supplementary without major IPD impact)	Variable: 7-days average daily spasm count at D21 Population: PP analysis set IES: Regardless permanent treatment discontinuation Regardless premature study discontinuation Without major IPD Regardless COVID-19 impact PLS: Mean difference between nabiximols and placebo Analysis: LSMD from observed value linear mixed-effect model for crossover data. No imputation under MAR assumption
	E4, SUP2 (Supplementary without COVID-19 impact)	Variable: 7-days average daily spasm count at D21 Population: FAS IES: Regardless permanent treatment discontinuation Regardless premature study discontinuation Regardless major IPD Without COVID-19 impact. PLS: Mean difference between nabiximols and placebo Analysis: LSMD from observed value linear mixed-effect model for crossover data. No imputation under MAR assumption
MSSS-88 total and sub scale scores	E5, Primary	Variable: Score at D21 Population: FAS IES: Regardless permanent treatment discontinuation Regardless premature study discontinuation Regardless major IPD Regardless COVID-19 impact PLS: Mean difference between nabiximols and placebo Analysis: LSMD from observed value linear mixed-effect model for crossover data. No imputation under MAR assumption
	E5, SUP1 (Supplementary without major IPD impact)	Variable: Score at D21 Population: PP population IES: Regardless permanent treatment discontinuation Regardless premature study discontinuation Without major IPD Regardless COVID-19 impact PLS: Mean difference between nabiximols and placebo Analysis: LSMD from observed value linear mixed-effect model for crossover data. No imputation under MAR assumption

	E5, SUP2 (Supplementary without COVID-19 impact)	Variable: Score at D21 Population: FAS IES: Regardless permanent treatment discontinuation Regardless premature study discontinuation Regardless major IPD Without COVID-19 impact. PLS: Mean difference between nabiximols and placebo Analysis: LSMD from observed value linear mixed-effect model for crossover data. No imputation under MAR assumption
P = Primary – S=Secondary - SA= Sensitivity analysis – SUP=Supplementary analysis		
E=Exploratory analysis		
FAS = Full analysis set – PP = Per Protocol		
PLS = Population-level summary.		
IES = Intercurrent event(s) strategy – IPD = Important protocol deviation;		
CFB = Change from baselines analysis. - OR= odds ratio - LSMD = Least square mean difference.		
MI = Multiple Imputation		
MAR = Missing at Random – MNAR = Missing not a random.		
MS = Multiple Sclerosis – NRS= Numerical rating scale		
LLMT-6 = Lower Limb Muscle Tone-6 - LLMT-4 = Lower Limb Muscle Tone-4		
LLMT-10 = Lower Limb Muscle Tone-10		
T25FW = Timed 25-foot walk

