10.17 Timed 25-Foot Walk

The T25FW is the time needed for a patient to walk 25-feet and will be performed at Day 1 H0 and D21 of each treatment period. The test consists of two trials separated by a 5-minute rest period. The maximum duration of each trial is set to 3 minutes (180 seconds).

The average T25FW (expressed in seconds) will be derived for each patient as the average of the two trials..

If a patient only performs 1 of the 2 trials at a given analysis day, the unperformed trial will be imputed using the highest T25FW (180 seconds) to perform the main analysis. An exploratory analysis will also be conducted without imputing unperformed trial as missing thus, leading to a missing average T25FW.

If a patient is not using the same device or is introducing a device within a given treatment period, the average T25FW will be set to missing.

The change and percentage change from baseline will then be calculated (as respectively described in [Section 10.3](#) and in [Section 10.4](#)).

The percentage change from baseline will be categorized as $\leq -20\%$ and $> -20\%$ to assess respectively $\geq 20\%$ improvement (as response) and $< 20\%$ improvement (as non-response) using imputed T25FW (as described above).

Missing average T25FW will be considered as not having met the improvement criteria (imputed as failure).

10.18 11-point Numerical Rating Scale Score (NRS-Spasticity Score)

The 7-day average 11-point NRS spasticity score will be derived for each patient as the mean NRS-spasticity score recorded in the eDiary during the last 7 days preceding Period 1 Day 1 H0 (Baseline), and Day 15 and D21 of each treatment period as follows:

Sum of the NRS spasticity scores during the 7 – day period

Number of days in which the daily diary was completed during the 7 – day period

For each assessment timepoint, the 7-day average 11-point NRS-spasticity score will be set to missing if scores are missing for 4 days or more in total or for 3 consecutive days within each 7-day period.

In case of the diary data are available but the visit does not take place the target visit date will be used.

On-treatment / off-treatment assessment

A 7-day average 11-point NRS spasticity score will be considered on-treatment if derived using only post baseline daily scores collected on or before the date of IMP discontinuation and will be considered off-treatment otherwise.

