12.5.5 Exploratory Efficacy Analysis

All exploratory efficacy analyses will be conducted among the full analysis set during the 51-day efficacy randomized period.

If more than 20% of patients from FAS are excluded in the PP Analysis Set; the analyses may be repeated using the PP analysis set as described in [Section 12.5](#).

The exploratory efficacy analyses based on LLMT-10 are described in [Section 12.5.5](#).

If at least 5 patients have at least one visit where the studied endpoint is impacted by the COVID-19, as assessed by the investigator, the analysis of that endpoint will be repeated excluding the concerned patients as described below:

- For the average 25-foot walk time (as described in [Section 10.2](#) and in [Section 10.17](#)) if during Period 1 and/or Period 2, D21 visit, T25FW trials are impacted by COVID-19,
- For the 7-day average NRS spasticity score (as described in [Section 10.2](#) and in [Section 10.18](#)) if during Period 1 and/or Period 2, Day 15 or D21 visits are impacted by COVID-19 and patient is infected*,
- For the 7-days average daily spasm counts (as described in [Section 10.2](#) and in [Section 10.19](#)) if during Period 1 and/or Period 2, Day 15 or D21 visits are impacted by COVID-19 and patient is infected*,
- For MSSS-88 total and sub-scales scores (as described in [Section 10.20](#)) if during Period 1 and/or Period 2 at D21 Visit MSSS-88 scoring is impacted by COVID-19.

* For eDiary endpoints, impact on COVID-19 is assessed based on information collected on the "Visit COVID-19 Impact" eCRF form. Thus if reason is due to "Caregiver or family member infected with COVID-19" but not to "Patient infected by COVID-19" the assessment will not be discarded.

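### Appendix 14 defines the T25FW per-protocol and COVID-19 analyses without the 180-second fill used in the main T25FW analysis, so a difference from the main result can come from the fill

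*SAP*

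**What the plan says.** Each T25FW visit has two timed walks, which the SAP calls trials, and the outcome is their average.

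- **SAP 10.17** caps each walk: "The maximum duration of each trial is set to 3 minutes (180 seconds". For the main analysis it uses that cap as the fill, under a condition: "If a patient only performs 1 of the 2 trials at a given analysis day, the unperformed trial will be imputed". Some averages can still be missing, for example after a change of assistive device. For the responder analysis the section adds: "Missing average T25FW will be considered as not having met the improvement criteria (imputed as failure".
- **SAP 12.5.5.1** analyses the change in this average with the crossover mixed model. It brings in non-imputed times only as a sensitivity analysis.
- **SAP 12.5.5** covers the repeats. If at least 5 patients are affected by COVID-19, "the analysis of that endpoint will be repeated excluding the concerned patients as described below". If more than 20% of the FAS is excluded from the PP set, "the analyses may be repeated using the PP analysis set as described in" Section 12.5.
- **SAP Appendix 14, E2 Primary**: "Single imputation at trial level: missing trial time are imputed to 180 seconds under MAR assumption".
- **SAP Appendix 14, E2 SUP2 (PP) and E2 SUP3 (COVID-19)**: "LSMD from CFB linear mixed-effect model for crossover data adjusted on period baseline average T25FW. No imputation under MAR assumption". The sensitivity row, "E2, S1 (without missing trial time imputation", carries the same analysis wording, so the meaning of no imputation is not in doubt.

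**The concern.** The PP and COVID-19 repeats are there to show whether protocol deviations or COVID-19 drive the walking result. A reader will naturally set them beside the main estimate, because Section 12.5.5 presents them as repeats. As Appendix 14 defines them, a retained patient with one unperformed walk also moves from an extreme filled value to a missing one. A gap between the main result and a repeat could then be put down to deviations or COVID-19 when part or all of it comes from the fill.

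Two smaller wording problems sit in the same rows. E2 Primary states the fill without the one-of-two condition of Section 10.17, so the two places do not describe the same dataset. It also attaches a MAR label to a fixed worst value.

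**Working it through.** The SAP gives no effect size, variance or sample size for T25FW, so there is no figure of the plan's own to reproduce. The check is a comparison of texts, followed by an illustration of size.

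**Step 1. Is the change of rule a pattern in Appendix 14?** Missing-data rule by row:

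| Endpoint | Primary row | PP repeat | COVID-19 repeat |
|---|---|---|---|
| LLMT-6 | placebo-based MI | same (SUP7) | same (SUP9) |
| LLMT-4 | placebo-based MI | same (SUP5) | same (SUP6) |
| LLMT-10 | placebo-based MI | same (SUP5) | same (SUP6) |
| **T25FW** | **180 s fill** | **no imputation (SUP2)** | **no imputation (SUP3)** |
| NRS spasticity | no imputation | same (SUP1) | same (SUP2) |
| Spasm count | no imputation | same (SUP1) | same (SUP2) |
| MSSS-88 | no imputation | same (SUP1) | same (SUP2) |

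Only T25FW changes its rule, and no reason is given.

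**Step 2. What does each T25FW comparison isolate?**

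- E2 Primary against SUP2 or SUP3: patients and fill both change.
- E2 Primary against S1: only the fill changes (both use the FAS and the same model).
- S1 against SUP2 or SUP3: only the patients change.

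**Step 3. Size of the fill.** Input from the documents: fill value 180 s (10.17). Completers, used only for scale: 68 after re-estimation and 46 as planned in the protocol (SAP 8.2). Assumptions: usual walk time t, every completer able to walk, and an unadjusted mean.

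- Filled average with one walk performed: (t + 180)/2. For t = 10 s this is (10 + 180)/2 = 95 s.
- Change from a baseline of t: (180 − t)/2. For t = 10 s this is +85 s.
- If the other N − 1 patients have mean change m, the arm mean is [(N − 1)m + 85]/N with the fill and m without it. The gap is (85 − m)/N, which is close to 85/N when m is small.
- One such record: 85/68 = 1.25 s, or 85/46 = 1.85 s.
- For t from 5 to 40 s: 87.5/68 = 1.29 s down to 70/68 = 1.03 s at N = 68, and 87.5/46 = 1.90 s down to 70/46 = 1.52 s at N = 46.

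A filled Day 21 record works against whichever treatment the patient was on. If no visit has exactly one performed walk, the shift is zero under the 10.17 rule.

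**The case against.** The strongest reply is that the planned set already contains what is needed. E2 S1 uses the FAS, the same model and no fill, so it separates the effect of the fill from the effect of the patients. That stands. A reader might infer that SUP2 and SUP3 cannot show whether deviations or COVID-19 matter; the documents do not support that, because set against S1 they can. What remains is that the SAP never says to use S1, and Section 12.5.5 points the reader to the endpoint's own analysis.

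The PP sentence in 12.5.5 is also plural and permissive, and T25FW has both a filled and an unfilled analysis. The conflict with the body text is therefore firmer for the COVID-19 repeat than for the PP repeat.

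On scope, a reader might infer from E2 Primary that a patient missing both walks scores 180 s, or that a non-ambulatory patient scores 180 s at every visit and contributes a change of zero. That reads an overview table literally. Section 12.5.5.1 takes its outcome from Section 10.17, which states the condition, and the schedule of assessments does not expect non-ambulatory patients to do the test.

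On the label, MAR may have been meant for averages still missing in the mixed model. That is a fair reading of the rows without imputation, but in E2 Primary the words are attached to the fill.

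On size, no document gives walk times, the number of walkers, or how often only one walk is done. Section 12.5.5.1 also plans a non-parametric analysis if residuals are not normal, which would limit the influence of an 85 s outlier. A reader might set the 1.25 s shift beside the 20% responder threshold, or infer that one filled record would reverse the result. The first compares an arm mean with an individual criterion. The second needs an effect and a spread that the documents do not supply.

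**Conclusion.** The point holds as an inconsistency within the SAP. Appendix 14 gives SUP2 and SUP3 a different outcome derivation from E2 Primary, against the sense of Section 12.5.5 and against its own practice for every other endpoint. A difference from the main T25FW result can therefore come from the fill unless the reader knows to compare with S1. The missing one-of-two condition and the MAR label are wording faults in the same table.

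The size is illustrative only: about 1.25 s per affected record, resting on the assumptions in Step 3. The reach is small. T25FW is exploratory and outside the multiplicity control, and both repeats run only if their thresholds (20% of the FAS, 5 patients) are met. No confirmatory conclusion changes. This is a minor point, worth correcting because the correction is cheap.

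**What to change.** In SAP Appendix 14:

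1. Define E2 SUP2 and E2 SUP3 on the same derived average T25FW as E2 Primary, so that only the patients differ. Optionally repeat S1 on the same subsets. At a minimum, if the versions without the fill are kept, state that they are to be compared with S1.
2. Limit the E2 Primary fill to visits where exactly one of the two walks was performed, as in Section 10.17.
3. Call the fill worst-value single imputation, and keep MAR only for averages that remain missing in the mixed model.

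The cost is appendix wording. Both derived variables, with and without the fill, are already specified, and no data collection changes.
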